- 5) If the date of a trial visit does not conform to the clinical trial protocol, subsequent visits should be planned to maintain the visit schedule relative to baseline.
- 6) The informed consent form must be signed prior to performing any protocol-related procedures, including but not limited to screening evaluations.
- 7) All subjects must use an emollient, as background treatment, twice daily (or more, as needed) for at least 14 days before baseline and must continue this treatment throughout the trial (including safety follow-up).
- 8) At trial visits, tralokinumab will be injected at the trial site, preferably by the subject or their caregiver, alternatively by site staff. At each trial visit from Week 4 onwards, subjects will be provided with tralokinumab to be administered at home until the next trial visit. In case of intercurrent illness that may compromise the safety of the subject, or fever within 72 hours prior to administration, tralokinumab administration should be rescheduled. If an anaphylactic reaction occurs, blood samples should be drawn for the analysis of serum tryptase (see details in Section 9.2).
- 9) At the first 3 tralokinumab dosing visits, subjects (or their caregiver) will be trained in how to inject tralokinumab, except for those who have already been trained in home use during the parent trial. In addition, if the subject and/or the caregiver is/are health care professional(s), no training is required, but the subject should be trained in how to handle the IMP according to the IMP handling manual and in the procedures to be followed in the event of an emergency. At the first 3 dosing visits, subjects (except for those who have received open-label tralokinumab treatment in the parent trial) will also be monitored for immediate drug reactions for a minimum of 30 minutes after dosing, with vital signs taken after 30 minutes or until stable, whichever is later.
- 10) IgE will not be measured at screening.
- 11) Urine samples will be tested with a dipstick at the trial site. A urine sample will be sent to the central laboratory for further analysis only if considered required by the investigator based on the dipstick results (Section 11.4.5).
- 12) Adult subjects from all parent trials, except the LP0162-1334 trial, will perform the DLQI. Subjects from the parent trial LP0162-1334 will perform the CDLQI, independent of the age of the subject during participation in ECZTEND.

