7.1.3 Treatment period (Week 0 and onwards)

7.1.3.1 Treatment initiation

Following the screening period, and at least 2 weeks after the last dose in the parent trial, subjects from all parent trials except the parent trial LP0162-1334, will receive an initial loading dose of 600 mg tralokinumab (4 mL) at baseline. Subjects from the parent trial LP0162-1334 will start with a dose of 300 mg tralokinumab (2 mL) at baseline. For the rest of the treatment period, all subjects will receive a dose of 300 mg tralokinumab Q2W (2 mL). Tralokinumab will be administered by subcutaneous (SC) injection.

Subjects will self-inject tralokinumab – or have tralokinumab injected by a caregiver – in their home after adequate training by site staff during the 3 first treatment visits (Weeks 0, 2, and 4). Subjects who already have experience with home use of tralokinumab from participation in open-label arms of trials LP0162-1325, -1326, and -1334 can start self-injecting at baseline without training (see also Section 9.2). At the trial visits, tralokinumab will be injected at the trial site, preferably by the subject or their caregiver, alternatively by site staff.

The first 3 treatment visits will also be used for post-dose monitoring for immediate drug reactions (see Section 9.2), as some subjects will have received placebo in the parent trial and are thus naïve to tralokinumab. Subjects who have transferred from the open-label trials LP0162-1342 or TRA-WEI-0015-I, or the open-label arms of trials LP0162-1325, -1326, or -1334, and who have received at least 3 doses of tralokinumab in the parent trial will not need to be observed.

Page 51 of 187

Subjects can use TCS (US class ≥ 4 or Europe class ≤ 3) or TCI at the investigator's discretion. If TCS are used, the subject should be monitored for signs of local or systemic TCS toxicity, and the safety and appropriateness of continued or repeated courses of TCS therapy should be evaluated by site staff.

Treatment is described in more detail in Section 9.

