7.1.3.3 Treatment period after May 2021

Subjects who wanted to participate in the trial after May 2021 had to re-consent (subjects included based on earlier protocol versions than version 10) or consent (subjects included based on protocol versions 10 to 12) to participate.

Subjects who re-consented/consented to participate in the trial after May 2021 follow the modified schedule of trial procedures specified in Section 4.2:

• For subjects included in the trial based on protocol versions 10 to 13, treatment will be initiated as described in Section 7.1.3.1.

Page 52 of 187

• For subjects included in the trial prior to protocol version 10, the first visit after May 2021 can be a site visit or a telephone visit. The first site visit may be after 8 weeks before starting the 16-week schedule to align individual visit schedules with endpoints.

- All subjects who re-consented/consented to participate in the trial after May 2021: subjects will start with a 24-week period with more frequent visits, and then continue with site visits (standard site visits or short site visits) every 16 weeks, interchanging with a telephone visit in between the site visits. For subjects from the parent trial LP0162-1334, the telephone visit should preferably be a video call. Visit types during the treatment period are described in Section 7.1.3.4.
- Treatment completion dates are dependent on the subject's consent and are done according to Panel 7.

Panel 7 Treatment completion date

Parent trial	Subject did NOT consent to continue after May 2021	Subject DID re-consent or consent to participate after May 2021
LP0162-1325, -1326, -1339, -1341, -1342, -1343, -1346, and TRA-WEI-0015-I	End of May 2021	Country-specific end date according to Appendix 3J
LP0162-1334 (adolescents)	End of May 2021	End of May 2022

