Subjects who already have experience with home use of tralokinumab from participation in open-label arms of trials LP0162-1325 or LP0162-1326 can start self-injection at baseline without training.

At trial visits, tralokinumab will be injected at the trial site, preferably by the subject or their caregiver, alternatively by site staff, when all assessments have been completed. It will be recorded in the eCRF (for trial visits only) whether tralokinumab was injected by the subject/caregiver or site staff.

Tralokinumab will be injected into the SC tissue of the upper arm, anterior thigh, or abdomen, separated by at least 3 cm within the same anatomical location. It is advised that the site of injection of IMP is rotated such that the subject receives IMP at a different anatomical part at each treatment. The injection site must be recorded in the source documents at each treatment visit and recorded in the eCRF.

Page 65 of 187

Further details on IMP administration are provided in a trial product handling manual. Subjects will also receive a pamphlet with instructions for IMP self-administration. IMP must be administered according to these instructions.

IMP dosing/dispensing visits are shown in the schedule of trial procedures (Section 4).

After administration of tralokinumab

For the first 3 tralokinumab dosing visits (Weeks 0, 2, and 4), subjects will be monitored for immediate drug reactions for a minimum of 30 minutes after administration of tralokinumab, with vital signs measured after 30 minutes or until stable, whichever is later. Vital signs will be documented in the eCRF. Subjects who have participated in open-label tralokinumab arms of trials LP0162-1325, -1326, or -1334, or from one of the open-label trials LP0162-1342 and TRA-WEI-0015-I, and who have received at least 3 doses of tralokinumab in the parent trial, are exempt from this monitoring.

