11.4.2 Vital signs

Vital signs (resting blood pressure, pulse, and body temperature) must be assessed according to the schedule of trial procedures (Section 4). Vital signs will be measured in a supine or sitting position following at least 5 minutes of rest.

For the first 3 tralokinumab dosing visits, subjects will be monitored for immediate drug reactions for a minimum of 30 minutes after administration of tralokinumab, with vital signs measured after 30 minutes or until stable, whichever is later (Section 9.2). Subjects who have participated in open-label tralokinumab arms of trials LP0162-1325, -1326, or -1334 or from one of the open-label trials LP0162-1342 and TRA-WEI-0015-I, and who have received at least 3 doses of tralokinumab in the parent trial, are exempt from this monitoring.

If an abnormal vital sign at screening is considered clinically significant by the investigator, it will be at the discretion of the investigator if the subject should be included in the trial (in accordance with exclusion criterion no. 28).

In case of abnormal findings, the vital sign measurement can be repeated approximately 15 minutes later with subjects resting in a supine or sitting position to verify the first measurement. Should the repeated measurement result in a normal value, the measurement must be repeated approximately 15 minutes after the second measurement with subjects resting in a supine or sitting position. If the third measurement verifies the second (normal) value, the first measurement should be considered false. If the third measurement confirms

the first measurement (abnormal), the second measurement will be considered false. Only the last value measured and considered correct will be recorded in the eCRF.

Reporting in eCRF

Vital signs and the date and time they were measured will be recorded in the eCRF. If vital signs were not assessed, a reason should be given. Clinically significant abnormal vital signs at the screening visit will be documented as medical history in the eCRF. At subsequent visits, any clinically significant deterioration of a pre-existing condition as well as any new clinically significant sign, symptom, or illness will be reported as an AE in accordance with Section 13.3.

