Appendix 3K: COVID-19

Rationale

The current COVID-19 pandemic warrants many subjects in the ECZTEND trial to stay at home to comply with authority-issued preventive measures. This impacts subjects' ability to attend site visits in person. To follow authorities' restrictions and to safeguard the subjects in the ECZTEND trial as well as providing continued therapy to secure the scientific integrity, this clinical trial protocol appendix is installed to provide an opportunity for telephone visits and courier delivery of IMP and pregnancy tests to subjects in replacement of the site visits. In addition, inclusion criterion 2 is changed during COVID-19 restrictions, to allow subjects who are not able to attend all protocol-mandated visits of their parent trials due to COVID-19 to participate in trial LP0162-1337, if considered eligible for continued treatment by the investigator.

Subject eligibility

Inclusion criterion 2 in trial LP0162-1337 states:

- Subjects must have completed* the treatment period(s) of one of the parent trials:
 LP0162-1325, -1326, -1334, -1339, -1341, -1342, -1343, -1346, or TRA-WEI-0015-I.
 - * To be assessed on the first day of IMP administration (baseline).
- In trial LP0162-1334, a subject is considered to have completed the treatment period, if the subject has attended the Week 52 visit on site.
- In trials LP0162-1343 and TRA-WEI-0015-I, a subject is considered to have completed the treatment period, if the subject has attended the Week 16 visit on site.
- Change to inclusion criterion 2 in trial LP0162-1337 during COVID-19 restrictions:

 The change to inclusion criterion 2 described in the following only applies to subjects coming

from parent trials LP0162-1334, -1343, and TRA-WEI-0015-I, as these are the only parent trials ongoing at the time of this appendix.

For subjects who are not able to attend the above-mentioned visits at site in their parent trials due to COVID-19, inclusion criterion 2 is considered fulfilled if AEs have been collected over the telephone and if the investigator has evaluated and documented that the subject is considered to benefit from continued treatment in trial LP0162-1337, despite the missed visit(s) in the parent trial.

Page 133 of 187

Version: 14.0

eCRF recording

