It must be recorded in the eCRF if a site visit was converted to a telephone visit (not applicable for the scheduled mandatory telephone visits in protocol version 13). This should be done in the comments log for each visit. 'Visit date' must also be documented.

If the subject is reached by telephone, use of emollients, AEs, concomitant medication and pregnancy test result (if applicable) must be collected. All other assessments should be marked 'Not done' in the eCRF, except for EASI, SCORAD, IGA, and weight, which should be left blank. The log line 'If not done, specify reason' in the assessment form must be answered with 'COVID-19' as well as the specific reason related to COVID-19, e.g. subject cannot visit site due to COVID-19 quarantine, or site is closed due to COVID-19.

In addition, the specific COVID-19-related reason for missing visit or performing visit as telephone visit must be entered in the 'Comments log' in the eCRF on subject level.

If no contact can be established between site and subject at a given visit, this must be recorded as a missed visit in the eCRF ("Not done"). The log line "If not done, specify reason" must be answered with the specific reason related to COVID-19, as above.

Description of visit scenarios

It is a requirement that all subjects attend the first 3 dosing visits (Visit 3, 4, 5) at the clinic according to protocol in order to ensure the 30 min. post-dose observation time for the 3 dosing visits. This will at the same time ensure proper training prior to home use. If attending the first 3 dosing visits is not possible, then the subject cannot take part in the trial.

Without compromising the safety of subjects and site personnel, it is expected that efforts are made to secure visit attendance at sites for visits Weeks 16, 56, 88, 104, 136, 152, 184, 216 and 248, in order to secure important efficacy assessments for the trial. Depending on national guidelines regarding COVID-19 and subject preferences, the remaining visits can follow 2 different scenarios as described below:

- 1) The subject is not restricted from attending visits at the clinic and continues to follow all procedures specified in the protocol.
- 2) Subject is not able to attend visits at the clinic, in which case the following procedure must be followed:
 - a. Site staff informs subject about the possibility of courier delivery of IMP and pregnancy test, if applicable.

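### Protocol Panel 5 footnote 9, its Panel 3 twin and the Section 5.6 note waive the 30-minute post-dose observation with no dose minimum, whereas Sections 7.1.3.1, 9.2 and 11.4.2 require three or more parent-trial doses

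*Protocol*

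**What the plan says.** At the first three dosing visits (Weeks 0, 2 and 4), subjects are watched for immediate drug reactions for at least 30 minutes, with vital signs taken afterwards. Some subjects who transfer from open-label treatment are excused, and the protocol describes that group in two ways.

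**No dose minimum.**
- Panel 5 footnote 9 (Protocol 4.2, the schedule after May 2021): "subjects (except for those who have received open-label tralokinumab treatment in the parent trial) will also be monitored for immediate drug reactions". The footnote marker sits on the tralokinumab administration cells for Weeks 0, 2 and 4.
- Panel 3 footnote 7 (Protocol 4.1, the schedule until end of May 2021) has the same wording.
- The asterisk note in Section 5.6 excuses transfers from the two open-label trials and three open-label arms because they are certain to have had tralokinumab. It mentions no number of doses, although the bullet it qualifies refers to Section 9.2 for details.

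**Three-dose minimum.**
- Section 7.1.3.1: transfers from the listed open-label trials or arms "and who have received at least 3 doses of tralokinumab in the parent trial will not need to be observed".
- Section 9.2: the same list, "and who have received at least 3 doses of tralokinumab in the parent trial, are exempt from this monitoring".
- Section 11.4.2: the same list, ending "TRA-WEI-0015-I, and who have received at least 3 doses of tralokinumab in the parent trial, are exempt from this monitoring".

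Section 7.1.3.3 ties the post-May-2021 schedule to the stricter rule: "For subjects included in the trial based on protocol versions 10 to 13, treatment will be initiated as described in Section 7.1.3.1".

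**The concern.** The two rules disagree for a subject who had open-label tralokinumab in the parent trial but only one or two doses in total. The footnote is what staff see beside the dosing cell, and it is the looser rule. I found no statement of whether the schedule or the body text prevails.

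At stake are the formal observation and the post-dose vital signs at up to three visits. Section 5.6 presents this monitoring as the precaution against hypersensitivity reactions. For every parent trial except LP0162-1334, the Week 0 dose is the 600 mg loading dose. A site that followed the footnote for such a subject would depart from Section 9.2 and so incur a protocol deviation.

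**Working it through.** There is no stated figure to reproduce. The check is a side-by-side reading of the current version 14.0 text, followed by simple dose counts to bound the affected group.

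**1. Side by side**

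| Place | Open-label exposure needed | Dose minimum |
|---|---|---|
| Panel 5 footnote 9 | yes | none |
| Panel 3 footnote 7 (historical) | yes | none |
| Section 5.6 asterisk note | yes (listed trials and arms) | none |
| Section 7.1.3.1 | yes (listed trials and arms) | 3 |
| Section 9.2 | yes (listed trials and arms) | 3 |
| Section 11.4.2 | yes (listed trials and arms) | 3 |

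**2. Apply both rules to an open-label transfer by total parent-trial doses**
- 3 or more doses: exempt under both rules.
- 1 or 2 doses: exempt under the footnote, observed under the three sections.
- No tralokinumab: observed under both rules.

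Only the middle case conflicts. The body sections count all tralokinumab doses in the parent trial, not only open-label ones, which narrows that case further.

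**3. Loss per affected subject**

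One observation at each of Weeks 0, 2 and 4, so at most 3.

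**4. Who could have only one or two doses?**

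Appendix 3K names LP0162-1334, LP0162-1343 and TRA-WEI-0015-I as the parent trials still ongoing when it was written. Of these, the Section 9.2 open-label list contains the LP0162-1334 open-label arm and TRA-WEI-0015-I. For LP0162-1343 and TRA-WEI-0015-I, "a subject is considered to have completed the treatment period, if the subject has attended the Week 16 visit on site"; for LP0162-1334 the corresponding visit is Week 52. The parent dosing schedules are not in the documents, so the counts below are assumptions.

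- TRA-WEI-0015-I, if dosed Q2W over Weeks 0 to 14: 14/2 + 1 = 8 doses. Having at most 2 means missing at least 8 − 2 = 6.
- TRA-WEI-0015-I, if dosed Q4W over Weeks 0 to 12: 12/4 + 1 = 4 doses. Having at most 2 means missing at least 4 − 2 = 2.
- LP0162-1334, if open-label Q2W dosing ran to Week 50 (50/2 + 1 = 26 occasions from Week 0): a placebo subject starting open-label treatment at Week 46 gets 3 doses (Weeks 46, 48, 50). Only a start at Week 48 or 50 leaves 2 or 1.

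Under these assumptions each route needs an unusual history: heavy non-adherence, or a very late switch from placebo.

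**The case against.** The strongest reply is that the group is close to empty by the protocol's own criteria. Inclusion criterion 2 requires a completed parent treatment period. Inclusion criterion 3 requires parent-trial compliance to the investigator's satisfaction, and a subject who missed most doses would hardly pass. The documents describe inclusion under protocol versions 10 to 13 (Synopsis, Section 7.1.3.3, Appendix 3B), whereas the current text is version 14.0, and Section 5.2 lists LP0162-1334 as completed. The footnote matters only for new starters, and the documents do not show that any remained. All of this stands as a limit on reach. It does not reconcile the two rules: completion is defined by visit attendance rather than doses, Appendix 3K relaxes even that for visits missed because of COVID-19, and recruitment is not stated to be closed.

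A second reply is that the looser rule has its own logic. Section 5.6 excuses these subjects because prior exposure is certain, and Section 7.1.3.1 justifies observation partly by the presence of tralokinumab-naïve subjects. That is a fair reading of why an exemption exists. But three operative sections add the dose count explicitly, so it looks deliberate.

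Third, the Panel 5 rows point to the right place. The administration row cites Section 9.2. The vital signs row carries no footnote 9 marker, schedules vital signs for everyone at Weeks 0, 2 and 4, and cites Section 11.4.2. This reduces the chance of error but does not correct the footnote.

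A reader might infer three stronger things:
- *That naïve subjects could go unobserved.* They could not; the footnote excuses only those who have had open-label tralokinumab.
- *That Appendix 3K makes the observation a condition of entry for subjects with one or two doses.* It asks for on-site attendance "in order to ensure the 30 min. post-dose observation time for the 3 dosing visits" and adds that "If attending the first 3 dosing visits is not possible, then the subject cannot take part in the trial". That attendance rule covers all subjects, including those properly exempt, so it shows the weight given to observation and settles nothing about the dose minimum.
- *That the safety results are affected.* The adverse event and vital signs analyses (Protocol 14.3.8, SAP 5.8) do not use the exemption.

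**Conclusion.** The inconsistency is real and sits in current text. Panel 5 footnote 9, Panel 3 footnote 7 and the Section 5.6 note omit a condition that Sections 7.1.3.1, 9.2 and 11.4.2 all impose. Because Section 7.1.3.3 sends post-May-2021 starters to Section 7.1.3.1, the three-dose rule is the one to take as intended.

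It is minor, and it is an error of drafting rather than of design. The affected group has no count in the documents, is probably very small, and may be empty. That judgement rests on inclusion criteria 2 and 3, on the lateness of version 14.0 and, for the dose counts, on assumed parent schedules. Residual risk is limited further: known or suspected hypersensitivity to the product and prior anaphylaxis to a biologic are exclusions, and doses at trial visits are given on site with emergency drugs at hand. The documents do not support a claim that any subject was in fact left unobserved.

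**What to change.** In Panel 5 footnote 9, extend the exemption so that it also requires the three parent-trial tralokinumab doses stated in Section 9.2, and cite that section. Make the same change in the Section 5.6 note; otherwise one of the looser statements would remain. Mirror it in Panel 3 footnote 7 for consistency only, since that schedule applied until end of May 2021.

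The cost is one clause in three places, with no new visit, procedure or data field. If no further subjects will start dosing, a short written clarification to sites that Section 9.2 governs is sufficient.
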